4.7 STUDY DISCONTINUATION

Palmetto Retina Center, LLC or Genentech may terminate this study at any time. Reasons for terminating the study may include the following:

- The incidence or severity of adverse events in this or other studies indicates a potential health hazard to subjects
- Subject enrollment is unsatisfactory
- Data recording is inaccurate or incomplete

4.8 STATISTICAL METHODS

4.8.1 Analysis of the Conduct of the Study

The analysis of complete data (36-month treatment period) for the study will be performed when all patients have either completed the visit at month 36 or discontinued early from the study, all data collected from the study are in the database, and the database is locked.

Interim analysis of data from the 12-month period will be performed when all patients have either completed the visit at month 12 or discontinued early from the study. Treatment assignment will be unmasked to the personnel performing the analysis when all data collected through month 12 are in the database and the data have been cleaned and verified. The Peto group sequential procedure ($Z \pm 3.0$ at all interim analyses) will be used to control for the possibility of type I error arising from the 12 month interim analysis.

For the primary objective, power calculations for different margins were undertaken. Familywise alpha of 0.05 was divided equally among three TOST (two one sided test) procedures ($\alpha=0.0167$): (1) comparing TREX vs. GILA in the 60 patients enrolled with bilateral disease, (2) TREX vs. control (total $n=90$, controls $n=30$), and (3) GILA vs. control (total $n=90$, controls $n=30$). A standard deviation of 11 letters was used for the power calculations and based from the RISE/RIDE data for subjects with DME. The power calculations suggests that the minimum boundary of equivalence for TREX vs. GILA that we can demonstrate is ± 7 letters (less than two lines of vision) and ± 9 letters (less than two lines of vision) for TREX and GILA vs. controls. Paired sample t-test will be used to compare TREX vs. GILA and two sample t-test will be used to compare the two groups vs. controls.

Because of the potential for confounding of the effect when comparing the control group (monthly cohort) to the TREX and GILA groups, we will use linear regression modeling with change in ETDRS as outcome

and cohort as main effect controlling for potential confounders (e.g., age, race, sex).

Adverse events, number of injections, and number of office visits will be approached statistically with descriptive analyses with point estimates and confidence limits provided. Exploratory linear, logistic, and time-to-event models will be used to analyze the other secondary outcomes.

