3.2 Rationale For Study Design

Diabetic macular edema (DME) is the most common cause of severe vision loss in Americans under 60. However, even mild to moderate vision loss from DME is impactful, since it strikes individuals often in the productive periods of their lives. Until now, interventions for diabetic retinopathy have been focused on maintaining current visual function or slowing the rate of vision loss.

The RISE and RIDE studies were parallel, phase III, double-masked clinical trials designed to evaluate the efficacy and safety of ranibizumab in the treatment of DME. In similarly designed protocols, patients were treated with monthly injections of ranibizumab (0.3 mg and 0.5 mg) versus sham monthly injections (all arms could receive macular laser photocoagulation from month 3 if meeting predefined criteria). The 2-year results demonstrated a statistically significant benefit from ranibizumab across numerous parameters, including mean change in visual acuity, percent of 10 letter and 15 letter gainers, and reduction in retinal thickness by OCT. Other smaller clinical trials have also demonstrated superiority of ranibizumab to laser alone.

Rationale for “Treat and Extend” versus fixed dosing

RISE and RIDE employed fixed dosing strategies during the entire 3-year mandatory treatment period. Like age-related macular degeneration, the best data available suggests that no alternative to monthly dosing has been

identified. However, monthly dosing of ranibizumab is problematic in DME for several reasons. First, compliance is often difficult in this population. In the RISE and RIDE studies, and multiple DRCR.net protocols, dropout rates consistently approach 10% per year. In addition, the natural history of DME suggests that long-term treatment will be required. This is quite different from age-related macular degeneration and retinal vein occlusion, where the disease activity wanes over time in many patients.

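### A Holm step-down would give the three primary equivalence tests more power than the flat 0.0167 at the same familywise 0.05; the equal split is valid, so this is a cheap improvement

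*Combined protocol and SAP*

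**What the plan says.** Section 4.8.1 is the only place that deals with multiplicity for the primary objective, and it does so within the power calculation: "Familywise alpha of 0.05 was divided equally among three TOST (two one sided test) procedures", giving 0.0167 each. The three procedures are:

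- a paired one, "comparing TREX vs. GILA in the 60 patients enrolled with bilateral disease";
- TREX vs control, 60 vs 30 eyes;
- GILA vs control, 60 vs 30 eyes.

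The controls are the Monthly cohort. On methods the section says: "Paired sample t-test will be used to compare TREX vs. GILA and two sample t-test will be used to compare the two groups vs. controls". On inputs: "A standard deviation of 11 letters was used for the power calculations". On results: "the minimum boundary of equivalence for TREX vs. GILA that we can demonstrate is ± 7 letters", with ±9 letters for each comparison with Monthly. Target power, assumed true difference and between-eye correlation are not given.

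Section 4.8.3 lists the endpoints without a multiplicity rule. No step-down, hierarchy or recycling of alpha appears anywhere. Section 3.2 says of earlier studies in this disease that "dropout rates consistently approach 10% per year", and section 4.8.4 analyses available cases without imputation.

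**The concern.** Under the equal split, a comparison that misses 0.0167 fails even when the other two have passed clearly. Holm releases the alpha of each passed test to those that remain. It needs no assumption about how the tests are correlated, so fellow-eye pairing and the shared Monthly arm do not affect its validity. Anything the equal split rejects, Holm also rejects.

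At stake is power for the comparisons of extended with monthly dosing, which rest on 30 Monthly eyes. Dropout reduces the analysed numbers directly, and 4.8.1 shows no allowance for it.

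**Working it through.** **Inputs from the documents.** Familywise alpha 0.05 over three TOSTs; SD 11; 60 pairs and 30 Monthly eyes; margins ±7 and ±9; paired and two-sample t-tests (all 4.8.1). **Assumed.** 80% power for reproducing the margins; true differences 0 unless stated; fellow-eye correlation 0 to 0.7; each TREX eye paired with a GILA eye of the same patient, and Monthly eyes independent of both.

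**1. Reproducing the plan.** Per-test alpha = 0.05/3 = 0.0167. With a true difference of 0, the smallest margin for 80% power is SE × (z(1−alpha) + z(1−beta/2)) = SE × (2.128 + 1.282) = SE × 3.410.

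- Against Monthly: SE = 11 × √(1/60 + 1/30) = 2.46, margin 8.39, rounded up to 9.
- TREX vs GILA at correlation 0: SE = 11 × √(2/60) = 2.01, margin 6.85, rounded up to 7.

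Both stated margins follow. Exact t-based TOST power at 0.0167 is 0.86 at ±9 and 0.80 at ±7.

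**2. What a later Holm step is worth.** Exact power of one comparison with Monthly at ±9 is 0.862 at alpha 0.0167, 0.903 at 0.025 and 0.953 at 0.05. Under Holm its power lies between the first and last figures, depending on how often the other tests pass.

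**3. Simulation of the two rules.** 100,000 trials per setting; the TOST p-value is the larger of the two one-sided p-values. The dropout case takes 10% per year for two years: 0.9² = 0.81, so about 48 of 60 and 24 of 30 remain, and SE against Monthly = 11 × √(1/48 + 1/24) = 2.75.

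| Setting | Test | Flat 0.0167 | Holm |
|---|---|---|---|
| 60 pairs, 30 Monthly, corr. 0 | each vs Monthly | 0.86 | 0.93 |
| same | TREX vs GILA | 0.80 | 0.91 |
| 60 pairs, 30 Monthly, corr. 0.3 | each vs Monthly | 0.86 | 0.93 |
| same | TREX vs GILA | 0.950 | 0.980 |
| 60 pairs, 30 Monthly, corr. 0.5 | each vs Monthly | 0.86 | 0.93 |
| same | TREX vs GILA | 0.993 | 0.998 |
| 48 pairs, 24 Monthly, corr. 0 | each vs Monthly | 0.72 | 0.83 |
| same | TREX vs GILA | 0.64 | 0.79 |
| 48 pairs, 24 Monthly, corr. 0.5 | each vs Monthly | 0.73 | 0.85 |
| TREX and GILA both 2 letters worse, 60/30, corr. 0 to 0.5 | each vs Monthly | 0.74 | 0.83-0.84 |

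At correlation 0.7, TREX vs GILA is already at about 1.00 under both rules.

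**4. Where the gain is small or absent.**

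- The chance of at least one success is identical (0.996 at correlation 0), because Holm's first step is also at 0.0167.
- With TREX truly 9 letters worse than Monthly and GILA equal to it, both comparisons that involve TREX are truly non-equivalent. GILA vs Monthly moves only from 0.862 to 0.864.
- With TREX at −9 and GILA at −2, GILA vs Monthly moves from 0.742 to 0.745.
- With one extension arm 3.5 letters better than Monthly and the other 3.5 worse, only TREX vs GILA is non-equivalent, exactly at its margin. Each Monthly test then rises from 0.53 to 0.57.

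**5. Error control.** The highest simulated familywise error under Holm in the null settings tried was about 0.043, below 0.05.

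**The case against.** The equal split controls familywise error. At full enrolment it already gives 80% and 86% power at the stated margins, in an open-label phase I/II trial. It also keeps decision and interval aligned: each test passes exactly when its 96.7% interval (1 − 2 × 0.0167) lies inside the margin, and the three intervals jointly cover with at least 1 − 3 × 0.0333 = 90% probability. Holm loses that match for its second and third decisions, which is a real cost for an equivalence claim. All of this stands, so it would be wrong to say that the equal split brings no benefit.

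The gain is also conditional, as step 4 of the working shows. A reader might infer that every test gains in every circumstance; it does not.

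A reader might also look at the chance that all three tests pass, which rises from 0.66 to 0.85 at correlation 0. Section 4.8.1 sets no such criterion. If it did, each test could be run at 0.05 with no split, and Holm would not be the remedy.

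Finally, the dropout case rests on background rates from other studies, and Holm only partly offsets the missing allowance. None of these objections removes the core: for any given data, Holm rejects at least what the equal split rejects, at the same familywise 0.05.

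**Conclusion.** The point holds as a cheap improvement. Power against Monthly rises by about 7 points at full enrolment, and by 10 to 12 points under the assumed dropout or with both extension arms 2 letters worse. For TREX vs GILA the gain is about 10 points at correlation 0, 3 at 0.3 and 0.4 at 0.5. These sizes rest on SD 11, the stated margins, and true differences and correlations that the documents do not give.

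Three stronger readings are not supported:

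- **That the equal split is an error.** It is valid, and the plan's own margins follow from it.
- **That shared patients and shared controls are the source of the gain.** Holm does not use the correlation; its gain comes from stepping down after a pass.
- **That the comparisons with Monthly sit at the edge of their margin.** The margin needed for 80% power is 8.39 letters against a stated 9.

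**What to change.** In 4.8.1, before any unmasking, replace the equal split with wording such as: the three TOST p-values will be ordered from smallest to largest and tested at 0.05/3, 0.05/2 and 0.05 in turn, stopping at the first failure. Keep the margins and the paired and two-sample t-tests. Still report the 96.7% interval for each comparison, and state that these intervals no longer map one-to-one to the second and third decisions.

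The timing matters because 4.8.1 unmasks the analysis personnel for the 12-month analysis. The text should also say how the step-down works alongside that look: 4.8.1 gives it a Z ±3.0 boundary, while 4.8.5 says that no formal schedule of interim analyses is planned.

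The cost is a short edit to the statistical section and the looser link between intervals and decisions. No extra eyes are needed.

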4. MATERIALS AND METHODS

4.1 SUBJECTS

4.1.1 Subject Selection

150 eyes from approximately 3 sites in the United States will be enrolled. Eligible subjects who have provided informed consent will be screened for eligibility before the initiation of any study procedures. Screening evaluations may be performed at any time within the 14 days preceding Day 0. These subjects must have center involved diabetic macular edema, with evidence of activity seen on SD-OCT.

(See attached Appendix A, the study flow chart, for screening assessments.)

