4.8.3 Efficacy Analyses

Primary Endpoint

- Mean change in ETDRS visual acuity at 24 months (week 92 – week 107) from Day 0.

Secondary Endpoints

- Incidence and severity of adverse events (ocular and non-ocular).
- Total number of intravitreal injections required during each year of the study period. In a separate proof of concept analysis, the number of intravitreal injections in the TREX and GILA cohorts over the 36-month study period will be compared with that of the other two cohorts ($p = 0.20$)
- Total number of office visits and imaging studies performed during each year of the study period (week 52, week 104, and week 156).
- Mean change in central foveal thickness per SDOCT from randomization to 12 months (week 46 – week 57), randomization to 24-months (week 92 – week 107), and randomization to 36 months (week 156)..
- Percentage of eyes gaining or losing 3 lines of vision or more and 1 line of vision or more at 6 months (week 22 – week 29), 12 months (week 46 – week 57), 18 months (week 70 – week 85), 24 months (week 92 – week 107), and 36 months (week 156) from Day 0.
- Noninferiority comparison (margin of 9 letters) of mean change in ETDRS vision from Day 0 to 24 months (week 92 – week 107) between the three study groups.

- The percentage of eyes which show progression of proliferative diabetic retinopathy requiring panretinal photocoagulation and/or pars plana vitrectomy over the 36-month study period.
- The percentage of eyes in the TREX and GILA cohorts who are eligible to begin the extension phase after 4 treatment visits.
- For TREX and GILA Cohorts, the time to achieve a “Secondary or Tertiary Baseline” retinal thickness.
- Percentage of eyes in each cohort that have shown a two-step change (increase and decrease) in diabetic retinopathy at 24 months and 36 months from day 0.

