4.8.4 Missing Data

Analyses of efficacy and safety will be based on available cases, without imputation for missing values.

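### The ±9-letter equivalence boundary against Monthly has room for no more than about 10% total loss by month 24; at the only dropout rate the protocol cites, power at ±9 would be about 73%

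*Combined protocol and SAP*

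**What the plan says.** Section 4.8.1 plans three equivalence comparisons: "Familywise alpha of 0.05 was divided equally among three TOST (two one sided test) procedures", so 0.0167 each. The first is "comparing TREX vs. GILA in the 60 patients enrolled with bilateral disease", by paired t-test. The other two set TREX and GILA (60 eyes each) against the 30 Monthly eyes, by two-sample t-test. The SD is 11 letters. The section gives "the minimum boundary of equivalence for TREX vs. GILA that we can demonstrate is" ±7 letters, and ±9 "letters (less than two lines of vision) for TREX and GILA vs. controls". It states no power target, no assumed true difference, no correlation between a patient's two eyes, and no expected number of eyes at month 24.

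Three other places bear on this:

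- Section 4.1.1: "150 eyes from approximately 3 sites in the United States will be enrolled". That is 30 + 60 + 60, the same numbers as in the power text.
- Section 4.8.4: "Analyses of efficacy and safety will be based on available cases, without imputation for missing values". Each eye without a month-24 value therefore reduces the analysed number.
- Section 3.2, on RISE, RIDE and several DRCR.net protocols: "dropout rates consistently approach 10% per year". This is the only dropout rate in the document.

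The 9-letter figure is used again as a secondary margin in Section 4.8.3: "Noninferiority comparison (margin of 9 letters) of mean change in ETDRS vision from Day 0 to 24 months".

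**The concern.** The boundaries are presented as what the trial can demonstrate, but they are computed on every enrolled eye, for an endpoint two years out, in a disease where the protocol itself reports substantial dropout. The SD is taken from RISE/RIDE; the dropout experience of the same trials is not carried into the power text.

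The comparison with Monthly is the exposed one, because the control arm starts with only 30 eyes and pairing does not help it. If loss is larger than ±9 can absorb, a failed equivalence test against Monthly could reflect too few eyes and not a difference between regimens. A reader who takes ±9 at face value would not know that.

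**Working it through.** **Inputs.** SD 11 per eye; one-sided alpha 0.05/3 = 0.0167 for each half of the TOST; 30 vs 60 eyes; 60 pairs (all Section 4.8.1). Assumed here because the plan is silent: true difference 0, equal loss in all arms, both eyes of a patient lost together, and 11 taken as the SD of change in a single eye.

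**Formulas.** Two-sample SE = 11·√(1/n₁ + 1/n₂). Paired SE = 11·√(2(1−ρ)/n), where ρ is the fellow-eye correlation. Power at margin M is the probability that |d| < M − t·(estimated SE), integrated over the chi-square distribution of the variance estimate. The 80%-power boundary is the M at which this equals 0.80.

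**Step 1: reproduce the plan's figures.**

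- Against Monthly: SE = 11·√(1/30 + 1/60) = 2.46 and t(88 df) = 2.162. The 80%-power boundary is 8.50, so ±9 is the next whole letter. Power at ±9 is 86.2%. As a normal-approximation check, 2.46 × (2.128 + 1.282) = 8.39.
- TREX vs GILA at ρ = 0: SE = 11·√(2/60) = 2.01. The 80%-power boundary is 6.98, and power at ±7 is 80.3%.

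Both stated figures are recovered at 80% power. At 90% power neither would be (±9.40, and ±7.73 at ρ = 0). A target of 85% with ρ between 0.1 and 0.3 would also give ±7 and ±9. So 80% is an inference, and the more lenient one: at 85%, ±9 is already just missed with 29 vs 58 eyes (84.5%).

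**Step 2: apply loss against Monthly.** Two-year retention is (1 − r)². At r = 10% it is 0.81, so 30 × 0.81 = 24.3 and 60 × 0.81 = 48.6, about 24 vs 49 eyes.

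| Loss per year | Eyes | SE | Power at ±9 | 80%-power boundary |
|---|---|---|---|---|
| 0 | 30 vs 60 | 2.46 | 86% | ±8.5 |
| 5% | 27 vs 54 | 2.59 | 80% | ±9.0 |
| 7.5% | 26 vs 51 | 2.65 | 78% | ±9.2 |
| 10% | 24 vs 49 | 2.74 | 73% | ±9.5 |

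Power at ±9 falls to exactly 80% at a total loss of 10.6%. If a few late leavers still give a value in the week 92–107 window (25 vs 50 eyes), power is 75% and the boundary is ±9.3.

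**Step 3: TREX vs GILA at ±7.** Power for ρ = 0 / 0.1 / 0.2 / 0.3:

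- 54 pairs: 73 / 80 / 86 / 92%
- 49 pairs: 66 / 73 / 81 / 88%

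The correlation needed for 80% power is 0.10 with 54 pairs and 0.19 with 49 pairs.

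**Step 4: the secondary noninferiority comparison.** With 24 vs 49 eyes, one-sided power at 9 letters is 86% at alpha 0.0167 and 90% at 0.025. The plan states no alpha for it.

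**Step 5: Holm in place of the equal split.** Simulated with 24/49/49 eyes, a shared Monthly arm, no true difference, and margins of ±7 and ±9:

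| ρ | Comparison | Equal split | Holm |
|---|---|---|---|
| 0 | TREX vs GILA | 66% | 80% |
| 0 | Each vs Monthly | 73% | 83% |
| 0.2 | TREX vs GILA | 81% | 90% |
| 0.2 | Each vs Monthly | 73% | 84% |

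**The case against.** The plan contains no arithmetic error, and a reader should not infer one: ±7 and ±9 follow from the stated inputs. Nor do the boundaries require every eye to be observed. Rounding ±8.5 up to ±9 leaves room for about 10% total loss against Monthly.

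The dropout rate is borrowed. Section 3.2 says that rates approach 10% a year in earlier trials, and cites this as a difficulty with monthly dosing. This trial tests regimens meant to lighten that burden, so the TREX and GILA arms might lose fewer eyes. That stands, but it does not remove the shortfall if Monthly itself loses 10% a year. Power at ±9 is then 75% with 5% a year lost in the other arm (24 vs 54), and 77% with none lost there (24 vs 60).

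The 80% target is inferred. The tolerated loss, ±9.5 and the 0.19 correlation depend on it; the fall in power from 86% to 73% does not.

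One might also conclude that TREX vs GILA is underpowered. The document does not support this. It gives no correlation and no reason to expect one below 0.19. If 11 were the SD of the paired difference, equivalent to ρ = 0.5, ±7 would survive the loss easily.

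Finally, the consequence is small for an open-label phase I/II study: ±9.5 is still under ten letters, so the two-line description remains true. This stands, and it limits the weight of the point.

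**Conclusion.** The point holds against Monthly, in a limited form. ±9 is right at full enrolment and tolerates no more than about 10% total loss by month 24. The cited rate, read at its upper end and applied equally to all arms, would bring power at ±9 to 73% and the 80%-power boundary to about ±9.5. At 7.5% a year the shortfall is slight, and at 5% a year there is none.

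These figures are conditional and are not a forecast: 73% should not be read as the trial's power. They rest on SD 11, no true difference, proportional loss and, for the boundaries, 80% power. No analysis becomes invalid, type I error is unaffected, and the 9-letter noninferiority comparison is less affected. For TREX vs GILA no deficiency is shown.

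**What to change.** 1. In Section 4.8.1, state the number of eyes expected to have a week 92–107 value, the power target and the fellow-eye correlation used. Restate the boundary against Monthly on those numbers, or give the power at ±9. At 80% power the boundary is ±9.0, ±9.2 and ±9.5 for loss of 5%, 7.5% and 10% a year.
2. Replace the equal 0.0167 split, which is valid, with Holm's step-down over the three TOSTs: order the three TOST p-values and compare them in turn with 0.0167, 0.025 and 0.05, stopping at the first failure. Familywise alpha stays at 0.05. With 24/49/49 eyes, power against Monthly rises from 73% to about 83–84%.

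Both are wording changes, with no added patients or visits. The costs are a slightly less favourable stated boundary against Monthly if loss above 5% a year is expected, and simultaneous confidence intervals that are less simple to present under Holm.

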3. STUDY DESIGN

3.1 DESCRIPTION OF THE STUDY

This is an open-label, phase I/II trial, which will assess the safety, tolerability and efficacy of a treat and extend management protocol for DME. Eyes which meet screening criteria will be enrolled into one of three treatment groups: (1) monthly intravitreal injections of 0.3 mg ranibizumab (Monthly Cohort, 30 eyes); (2) monthly intravitreal injections of 0.3 mg ranibizumab for 4 visits, followed by a “Treat and Extend” protocol based on pre-specified criteria of disease activity (T-REX cohort, 60 eyes); (3) monthly intravitreal injections of 0.3 mg ranibizumab for 4 visits combined with adjunctive Guided focal Laser photocoagulation to microaneurysms at week 4 and then every 3 months if leakage is present on fluorescein angiography, followed by a treat and extend protocol based on pre-specified criteria of disease activity (GILA cohort, 60 eyes).

Randomization Scheme:

All eyes which satisfy all inclusion/exclusion criteria will be randomized 1:2:2 into the Monthly:TREX:GILA Cohorts.

3 Treatment arms:

1. Monthly Cohort (30 eyes): Monthly intravitreal injections of 0.3 mg ranibizumab for 36 months, unless they meet pre-specified criteria for PRN treatment (indicated below). Treatment will begin at Day 0 and

subsequent study visits should be scheduled to occur every 28 (± 7) days relative to the date of the first injection. Dosing should not occur earlier than 21 days after previous treatments.

Starting at week 104, study eyes will have the opportunity to undergo treatment on a pro re nata (PRN) basis. Thus, eyes who have a central subfield thickness (CST) ≤ 325 microns at the week 104 visit, will not be given treatment at week 104. Eyes will continue to be seen every 4 weeks and will be given an intravitreal injection of ranibizumab 0.3 mg only if the CST is > 325 microns. Eyes will also receive treatment if there is a > 5 letter loss due to DME (compared to the vision at week 104), regardless of thickness on OCT.

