4.1.2 Inclusion Criteria

Subjects will be eligible if the following criteria are met:

- Ability to provide written informed consent and comply with study assessments for the full duration of the study
- Age \geq 18 years of age
- Patient-related considerations
- For sexually active women of childbearing potential, agreement to the use of an appropriate form of contraception (or abstinence) for the duration of the study
- Although no birth control method is 100% effective, the following are

considered effective means of contraception: surgical sterilization, use of oral contraceptives, barrier contraception using either a condom or diaphragm with spermicidal gel, an intrauterine device, or contraceptive hormone implant or patch. A patient's primary care physician, obstetrician, or gynecologist should be consulted regarding an appropriate form of birth control.

- Ability and willingness to return for all scheduled visits and assessments

Disease-related considerations

- The presence of center-involving diabetic macular edema on clinical exam and SD-OCT
- Best corrected visual acuity in the study eye, using ETDRS testing, between 20/25 and 20/320 (Snellen equivalent), inclusive.
- Clear ocular media and adequate pupillary dilation to permit good quality fundus imaging.

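### The t-tests of 24-month ETDRS change carry no covariates and the added regression's open list does not name Day-0 acuity; pre-specifying Day-0 letters would probably narrow the equivalence intervals and raise power

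*Combined protocol and SAP*

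**What the plan says.** The primary endpoint is change in ETDRS letters from Day 0 to 24 months. Section 4.8.1 splits a familywise alpha of 0.05 over three TOST procedures, 0.0167 each. TREX and GILA are compared by paired t-test, "comparing TREX vs. GILA in the 60 patients enrolled with bilateral disease". For Monthly, a "two sample t-test will be used to compare the two groups vs. controls". None of these tests has a covariate.

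A separate paragraph adds a linear regression, with this reason: "Because of the potential for confounding of the effect when comparing the control group (monthly cohort) to the TREX and GILA groups". Change in ETDRS is the outcome, "and cohort as main effect controlling for potential confounders (e.g., age, race, sex". No TOST, alpha or margin is attached to it, and no adjusted model is given for TREX vs GILA.

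Day-0 acuity is not named as a covariate or stratification factor anywhere. Section 4.2 gives only the 1:2:2 ratio. The entry criterion in Section 4.1.2 is wide: "Best corrected visual acuity in the study eye, using ETDRS testing, between 20/25 and 20/320 (Snellen equivalent), inclusive".

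**The concern.** Equivalence is declared only if the whole interval lies inside the margin, so an interval wider than necessary costs power. With 30 Monthly eyes, that cost falls on two of the three primary comparisons. The baseline value of the outcome is an obvious candidate for removing residual variance, and the plan does not use it as a covariate. Subtracting it to form the change score removes only part of what a regression on it can remove.

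The second issue is that the regression's covariates are illustrative and the plan does not say in words whether the t-test or the regression settles the comparisons with Monthly. The deciding model should not be open to choice once results are visible.

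**Working it through.** **Inputs from Section 4.8.1:** SD 11 letters, taken here as the raw SD of change; alpha 0.05/3 = 0.0167, used for each one-sided test; 30 vs 60 eyes at ±9; 60 pairs at ±7. **Assumed:** true difference 0; uncorrelated changes in the two eyes of a pair; r from 0 to 0.5 (only its size matters); baseline differences between cohorts due to chance alone.

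**Plan's own figures.** The standard errors are 11 × √(1/30 + 1/60) = 2.46 against Monthly and 11 × √(2/60) = 2.01 for the pairs. The plan states no power level. At 80% the smallest margins that can be shown are 8.50 and 6.98 letters, which round up to the stated 9 and 7. Halving alpha to 0.00833 per side gives 9.19 and 7.57, which do not match. The boundaries therefore reproduce, and 0.0167 per one-sided test is the reading that fits.

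**Unadjusted.** Half-width = t × SE.
- Against Monthly: 2.162 × 2.46 = 5.32 letters (88 df), power 86.2% at ±9.
- Pairs: 2.179 × 2.01 = 4.38 letters (59 df), power 80.3% at ±7.

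**Adjusted for Day-0 letters.** The residual SD is 11 × √(1 − r²). One degree of freedom is lost, and the variance is inflated for chance imbalance by 1 + 1/86 (30 vs 60) or 1 + 1/57 (pairs). For the pairs the covariate is the between-eye difference in Day-0 letters, and r is its correlation with the between-eye difference in change.

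| Assumed r | vs Monthly: half-width | vs Monthly: power at ±9 | Pairs: half-width | Pairs: power at ±7 |
|---|---|---|---|---|
| unadjusted | 5.32 | 86.2% | 4.38 | 80.3% |
| 0 | 5.35 | 85.6% | 4.42 | 79.2% |
| 0.2 | 5.24 | 87.6% | 4.33 | 81.6% |
| 0.3 | 5.10 | 89.8% | 4.21 | 84.5% |
| 0.5 | 4.63 | 95.6% | 3.82 | 92.5% |

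Interval and power move together. Where the interval narrows, power rises. Where power falls, the interval has widened. Break-even |r| is 0.11 against Monthly and 0.13 for the pairs.

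**With dropout.** Section 3.2 cites losses near 10% a year in earlier studies. Retention of 0.9 × 0.9 = 0.81 leaves about 24 vs 49 eyes. Power is then 73.0% unadjusted, against 72.0%, 74.8%, 78.3% and 88.5% adjusted at r = 0, 0.2, 0.3 and 0.5 (break-even 0.12). For 49 pairs it is 65.6% unadjusted and 63.9% at r = 0 (break-even 0.15).

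**If Monthly eyes differ systematically.** Suppose Day-0 acuity differs between cohorts by 0.5 SD (assumed). The variance inflation rises from about 1.01 to 1.07, break-even |r| rises to about 0.25, and adjusted power at r = 0.2 is 84.9%, below the t-test's 86.2%. The estimate also moves, by r × 11 × 0.5 letters: 1.65 at r = 0.3 and 2.75 at r = 0.5.

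**The case against.** **The figures assume that the cohorts differ only by chance.** The plan justifies its regression by possible confounding against Monthly, and it pairs TREX and GILA within bilateral patients. Section 4.2 describes a plain 1:2:2 randomisation of eyes, and the documents do not reconcile the two. This stands. If the difference is systematic, adjustment becomes a question of bias as well as precision, and removing age, race and sex from view would defeat the regression's purpose. A closed confounding analysis therefore has to be kept and reported.

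**The gain depends on an r that is not given.** This also stands. A reader might try to derive r. If acuity had the same SD at Day 0 and month 24, r would be −11/(2 × Day-0 SD), or −0.55 to −0.39 for SDs of 10 to 14. The only SD in the documents is "A standard deviation of 11 letters was used for the power calculations and based from the RISE/RIDE data for subjects with DME". Equal SDs and a Day-0 SD of 10 to 14 are outside assumptions, and the gain disappears if the month-24 SD is about 20% to 40% wider. A large gain cannot be claimed.

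**The t-tests are the natural primary analysis.** The paragraph that sets alpha and margins ends by naming them, and the regression follows separately. A reader might still infer inflated type I error, because "This is an open-label, phase I/II trial" and "Treatment assignment will be unmasked to the personnel performing the analysis when all data collected through month 12 are in the database". In simulation at a true difference of 9 (30 vs 60 eyes), always taking the more favourable of the t-test and the age/race/sex model gives 0.018 to 0.022 instead of 0.0167. Choosing among all 16 subsets of Day-0 letters, age, race and sex gives 0.027 to 0.032. These are worst cases for a choice that the plan does not say it will make. They do not apply to TREX vs GILA, which has no planned regression. Any single fixed model holds 0.0167.

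**The list is open.** Day-0 acuity is therefore unnamed but not excluded. This is correct: the gap is in pre-specification.

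**Conclusion.** The point holds as a recommended improvement. The planned t-tests are valid under true randomisation, and the ±7 and ±9 margins reproduce. Nothing here shows bias in the tests or an error in the margins.

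Pre-specifying Day-0 letters would probably narrow the intervals and so raise power. Against Monthly the change runs from −0.6 point (r = 0) to +9.4 points (r = 0.5), and for TREX vs GILA from −1.1 to +12.2 points. The loss occurs only if |r| is below about 0.11 to 0.15, and is somewhat larger with dropout: 1.0 to 1.1 points at 24 vs 49 eyes and about 1.8 at 49 pairs. It would be wrong to infer that tighter intervals are bought with power, because at a fixed margin the two improve together.

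All of this rests on SD 11 being the raw SD of change, a true difference of 0, an assumed r and, for the pairs, uncorrelated changes. The figures do not apply if Monthly eyes differ systematically from the bilateral TREX and GILA eyes. Adjustment then also changes the estimate.

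**What to change.** In Section 4.8.1:

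1. For TREX vs Monthly and GILA vs Monthly, apply the TOSTs at 0.0167 to a linear model of 24-month change on cohort, with Day-0 ETDRS letters as the pre-specified covariate.
2. For TREX vs GILA, adjust the paired difference in change for the between-eye difference in Day-0 letters.
3. State that these analyses decide equivalence.
4. Replace the illustrative list with a closed one (Day-0 letters, age, race, sex) for one pre-specified confounding analysis against Monthly. Report it and the unadjusted t-tests beside the deciding model.

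The cost is a few sentences and no new data, since Day-0 letters are needed for the endpoint. Statistically it is one degree of freedom plus the small imbalance term. Age, race and sex are kept in the reported confounding analysis and out of the deciding model. If they are not prognostic, adding them there (four covariate terms in all) would give 83.8% power against Monthly at r = 0, which is 2.4 points below the t-test. If the Monthly cohort proves systematically different, the side-by-side report shows how far the contrast moves.
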